13.4 Endometrial Biopsy, Ultrasound, Sonohysterography, Hysteroscopy

Screening and gynecologic evaluations will be performed by a qualified and trained investigator and include endometrial biopsy, transvaginal ultrasound, sonohysterography or hysteroscopy to verify eligibility and prior to conducting the treatment procedure. Screening ultrasounds will be interpreted by experienced investigators using inclusion and exclusion criteria.

Record the reference uterine sounding depth measurement. Once these tests are completed, the patient must not undergo any other gynecological procedures prior to the Minitouch procedure.

13.5 Vital Signs

Vital signs including systolic blood pressure, diastolic blood pressure, temperature, respiratory rate, and pulse rate will be measured according to the Schedule of Events after at least 5 minutes at rest in the sitting or supine position.

13.6 Concomitant Medications

The use of concomitant medications is reviewed with the patient according to the Schedule of Events. Any changes in medication from the time of consent to the end of study should be recorded in the Concomitant Medications eCRF.

13.6.1 Screening and Follow-up

During screening, all medications should be captured, thereafter, any medication changes through the end of study should be recorded in the Concomitant Medications eCRF.

Note that any intermittent ("PRN") use of medication, or any new prescribed medication in follow-up may indicate the occurrence of, or a change to an ongoing Adverse Event.

13.6.2 Contraception

The patient must be on a reliable method of contraception for the duration of the study. Special attention should be paid to medication review of hormonal contraception since the patient must have been on said method for \geq 3 months prior to the onset of the screening menstrual cycle used for PBLAC diary completion and must remain on the same hormonal regimen through the 12-month follow-up visit.

CONFIDENTIAL & PROPRIETARY

Also, a subject may not begin hormonal contraception during the follow-up period if she were not on one at the time of screening.

13.7 Adverse Events

Serious adverse events (SAEs) and adverse events (AEs) are collected from the time of enrollment (on the day of the Minitouch procedure). Information on the collection and reporting of AEs and SAEs can be found in **Section 14 ADVERSE EVENT REPORTING.**

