12.2 Validity Windows for Baseline Testing

All Baseline activities, including prescreening and rescreening testing must be conducted within the validity window. Review testing dates prior to procedure to ensure that all required activities have been conducted within window as outlined in **Table 12-1** below.

For example, the assessment of the patient's medical and surgical history must have occurred no more than 6 months prior to the date of treatment. If that assessment is outside of that validity window, then reassess the subject's medical and surgical history prior to the procedure.

| Table 12-1: Validity Windows | | |
|--|---|--|
| Screening Activity | Validity Window (where 6 months = 180 calendar days; and 12 months = 365 calendar days) | |
| Demographics | 6 Months | |
| Medical and surgical history | 6 Months | |
| Documented history of excessive menstrual bleeding | 6 Months | |
| Physical examination | 6 Months | |
| Pap-Smear | 12 Months | |
| Transvaginal ultrasound | 6 Months | |
| Endometrial biopsy | 12 Months | |
| Sonohysterography / hysteroscopy | 6 Months | |
| Complete Blood Count | 6 Months | |
| Serum FSH | 6 Months | |
| Urine Pregnancy Test | 6 Months | |

Page 32 of 65

CONFIDENTIAL & PROPRIETARY

| Table 12-1: Validity Windows | | | |
|--|--|--|--|
| Screening Activity | Validity Window (where 6 months = 180 calendar days; and 12 months = 365 calendar days) | | |
| Urine Dipstick Pregnancy Test (Day of Procedure) | 24 Hours | | |
| STD Tests | 6 Months | | |
| PBLAC | 6 Months* | | |
| Menorrhagia Impact Questionnaire | 6 Months | | |
| Dysmenorrhea-related pain | 6 Months | | |

* If the qualifying PBLAC diary was completed more than 3 months prior to the date of planned treatment, the investigator must verbally confirm with the subject that she continues to experience heavy menstrual bleeding, i.e., there has not been a clinically significant change in her menstrual status. It will be left to the investigator's judgment whether another monthly PBLAC diary is warranted to reconfirm eligibility prior to treatment.

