13.11.2 Administering PBLAC Diaries

During Screening

If a patient has undergone a procedure (e.g., polyp removal, fibroid removal, IUD removal, etc) that could affect menstrual bleeding, the screening PBLAC may be administered after 30 days from the date of that procedure.

If a patient discontinued taking oral hormonal contraception, the screening PBLAC may be administered after a washout interval of at least 90 days from the last dose of the hormonal contraception.

If a patient is currently on hormonal medication for heavy menstrual bleeding, the patient must discontinue the medication. The screening PBLAC may be administered after a washout interval of at least 90 days from the last dose of the hormonal medication.

During Follow-Up

PBLAC diaries will be distributed and collected through the 12-month follow-up (365 days or 1-year anniversary); accordingly, 13 PBLAC diaries are expected to be collected during the study follow-up. In between visits, participants should return their diaries (in person or by mail) every month upon completion. Electronic scans or photos of diaries are permitted to be submitted monthly, however, the original diaries must still be submitted to the site and retained in the study records as source documents.

At a minimum, the PBLAC diary will be reviewed with the patient at each follow-up visit, and any needed additional sanitary products provided. Confirmation of understanding and/or retraining patients on PBLAC diary completion throughout follow-up is encouraged.

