18.2 Data Collection and Electronic Case Report Form Completion

All study data will be collected and recorded by authorized study personnel on the required electronic Case Report Forms (eCRFs). Identifiable patient information will not be recorded in the eCRFs. Patients will be assigned unique study identification numbers. Only study site personnel directly involved with study and Sponsor, monitors or designee(s) will have access to the documentation that links the study identification numbers to identifying patient information.

The eCRFs will capture information relevant to the patients' clinical presentation, medical history, laboratory values, and results of clinical and/or gynecological testing. Follow-up clinical data will include laboratory assessments, current medications, physician office visits, hospitalizations, and/or adverse events that have occurred since study enrollment or from the prior visit.

The site PI will be required to sign and date the completed eCRFs on the appropriate page(s) to verify that he/she has reviewed the recorded data, and assures its accuracy and completeness.

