23 SCHEDULE OF EVENTS

| Table 23-1: Schedule of Events | | | | | | | | |
|---|-------------------------|-------------------------|----------------------------|----------|-----------|-----------|-----------|-------------------|
| Assessments ² | Screening / Baseline | Procedure/ Discharge | SOC 24- hour contact | Week 2 | Month 3 | Month 6 | Month 12 | Months 24 & 36 |
| Validity Windows | Various ³ | Day 0 | 18-48 hours | ± 7 days | ± 2 weeks | ± 2 weeks | ± 4 weeks | ± 8 weeks |
| Informed Consent ⁴ | х | | | | | | | |
| Demographics | х | | | | | | | |
| Medical and surgical history (including documented history of excessive menstrual bleeding) | x | | | | | | | |
| Physical examination ⁵ | х | | | | | | | |
| Pap-Smear ⁶ | х | | | | | | | |
| Endometrial biopsy ⁷ | х | | | | | | | |
| Transvaginal ultrasound/ Sonohysterography /hysteroscopy ⁸ | x | | | | | | | |
| Vital Signs ⁹ | | х | | | | | | |
| Complete Blood Count | х | | | | | | | |
| Serum FSH | х | | | | | | | |
| Urine Pregnancy ¹⁰ , ¹¹ | х | х | | | | | | |
| Minitouch Procedure | | х | | | | | | |
| Con. Medications/ Treatments ¹² | Х | Х | х | Х | Х | Х | х | Х |

² If a patient terminates from the study during a visit, site will attempt to complete all assessments, and review Early Termination section requirements for additional testing.

³ See Section 12.2 for screening validity windows. Reassess dates of all study requirements prior to procedure to ensure that none are out of window.

⁴ The informed consent process and signatures must precede any study-specific test or medication change.

⁵ PE at Baseline includes pelvic and abdominal exam, height, weight, BMI. Note height, weight, and BMI are required only at screening.

⁶ Results from previous pap-smear may be used if done within 12 months of treatment.

⁷ Results from the endometrial biopsy may be obtained from a prior biopsy result if done within 12 months of treatment.

⁸ At least one gynecological diagnostic test is required. Measure uterine sounding depth, cervix length and cavity length.

⁹ Vital signs to include temperature, pulse, respiratory rate and blood pressure after at least 5 minutes at rest in the sitting or supine position.

¹⁰ Pregnancy test must be negative during screening and on day of procedure prior to procedure initiation. Also, if study patient becomes amenorrheic at any time post-procedure, a urine pregnancy test should be administered.

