¹¹ Conduct urine pregnancy tests as needed during follow-up; conduct STD tests as needed.

¹² Special attention should be paid to medication review of contraception since patient must have been on said method for \geq 3 months prior to enrollment and must remain on the same hormonal regimen through the 12-month follow-up visit.

May not be reproduced, disclosed, or used in any form or by any means without written permission of an authorized representative of MicroCube, LLC. Hardcopies for reference only.

| Table 23-1: Schedule of Events | | | | | | | | |
|--|-------------------------|-------------------------|----------------------------|----------|-----------|-----------|-----------|-------------------|
| Assessments ² | Screening / Baseline | Procedure/ Discharge | SOC 24- hour contact | Week 2 | Month 3 | Month 6 | Month 12 | Months 24 & 36 |
| Validity Windows | Various ³ | Day 0 | 18-48 hours | ± 7 days | ± 2 weeks | ± 2 weeks | ± 4 weeks | ± 8 weeks |
| Patient PBLAC Training ¹³ | х | х | | | | | | |
| Screening PBLAC ¹⁴ | х | | | | | | | |
| Distribute PBLAC Diary and Product ¹⁵ | х | х | | х | х | х | | |
| PBLAC Diary Collection | х | | | | х | х | х | |
| Final Eligibility Assessment ¹⁶ | | х | | | | | | |
| Menorrhagia Impact Questionnaire | х | | | | х | х | х | х |
| Dysmenorrhea-related pain | Х | | | | Х | Х | Х | х |
| Procedure-related pelvic pain ¹⁷ | | х | х | | | | | |
| Patient Global Evaluation (PGE) | | | | | х | х | х | х |
| Investigator Global Evaluation (IGE) | | | | | х | х | х | х |
| AE / SAE / UADE ¹⁸ | | х | х | Х | х | х | Х | х |

¹⁶ Eligibility criteria will be assessed at baseline and reconfirmed prior to procedure initiation. Only patients who meet all eligibility criteria at that time will be included.

¹⁷ Pelvic pain (utilizing the NRS) will be evaluated BEFORE (prior to administration of procedure meds) and AFTER the procedure at discharge and during the SOC 24-hour telephone contact).

¹⁸ AE / UADE / SAE collection starts after subject is enrolled (on the day of the Minitouch procedure).

Page 60 of 65

CONFIDENTIAL & PROPRIETARY

Page 61 of 65

CONFIDENTIAL & PROPRIETARY

Page 62 of 65

CONFIDENTIAL & PROPRIETARY

| ATTACHMENT B: | SAMPLE MENORRHAGIA | IMPACT QUEST | IONNAIRE (MIQ) |
|---------------|--------------------|--------------|----------------|
|---------------|--------------------|--------------|----------------|

| MIQ concept | MIQ item | | Response scale |

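### Adverse event collection opens on the procedure day, so serious harm from study-required steps between consent and treatment falls outside it

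*Combined protocol and SAP*

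**What the plan says.** **When collection starts.** Section 13.7 reads: "Serious adverse events (SAEs) and adverse events (AEs) are collected from the time of enrollment (on the day of the Minitouch procedure"). Footnote 18 to Table 23-1 reads: "AE / UADE / SAE collection starts after subject is enrolled (on the day of the Minitouch procedure"). The adverse event row of that table is blank under screening. Section 18.2 has the case report forms capture "adverse events that have occurred since study enrollment or from the prior visit". Sections 10 and 11.9 place enrollment on the treatment day, once eligibility is confirmed.

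**What happens between consent and that day.** Sections 11.2 and 12.3 allow protocol-driven tests and medication changes only after consent. Two kinds of step follow:

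- *Stopping treatment.* Section 13.11.2: "If a patient is currently on hormonal medication for heavy menstrual bleeding, the patient must discontinue the medication". It continues: "The screening PBLAC may be administered after a washout interval of at least 90 days from the last dose of the hormonal medication".
- *Screening tests.* Section 13.4 says the evaluations "include endometrial biopsy, transvaginal ultrasound, sonohysterography or hysteroscopy to verify eligibility and prior to conducting the treatment procedure". Footnote 8 to Table 23-1 sets the minimum: "At least one gynecological diagnostic test is required". In-window results from routine care may be reused (11.2, 12.2, footnote 7), and 12.3 tells sites to keep invasive testing low.

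**What happens to events in that period.** Under 12.3.3 a woman who leaves before treatment is a screen failure, and 11.9 asks for an EDC entry saying why she did not take part. In a woman who is later treated, 14.1.5 classes anything recorded and diagnosed before the procedure as pre-existing unless it worsens to a clinically significant degree.

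**The concern.** The study itself imposes risk before it starts to look for harm. A woman who gives up hormonal treatment for heavy bleeding in order to qualify is left for months without that treatment for the condition that brought her to the trial. A biopsy done only to establish eligibility carries its own complications. If either step puts her in hospital with a serious deterioration, the event would meet the seriousness criteria in 14.1.2. It would still fall before the date on which the protocol begins collecting adverse events.

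What is at stake is oversight of the screening phase. If washout or a screening test were causing serious harm, the sponsor and IRB would want an early, structured signal so that the rule could be changed. As written, they might learn of it late or only in fragments.

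**Working it through.** The protocol gives no figure to reproduce. The check compares sections, with one short sum.

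**1. Does any wording move the start date earlier?**

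- *Consented-enrolled women.* Section 11.9 uses this label for consented women who are not treated, so enrollment might seem to begin at consent. The parenthesis in 13.7 and footnote 18 ties collection to the procedure day and closes that reading.
- *The 24-hour rule in 14.3.* It gives no start date, and neither do 14.1.2 and 14.2.3. None of them displaces the explicit start in 13.7. Notification under 14.3 runs through the case report forms, which 18.2 scopes to events since enrollment or the prior visit.
- *Termination visit, 12.10.* It lists serious adverse events for women who leave before Month 12, but a woman who leaves before treatment is a screen failure under 12.3.3. Nothing in 12.10 extends collection to her.
- *Causality scale, 14.2.4.* It covers the device, a malfunction or the procedure. Harm from a screening test or from stopping a drug has no matching category.

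**2. What traces would remain?** Medication changes from consent onward (13.6), baseline history and symptoms (14.2.3), outside-physician records kept at the site (18.1), a withdrawal reason and, arguably, a withdrawal report to the IRB (11.8.1). None is an adverse event record with severity and causality.

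**3. Who is exposed?**

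- *Washout:* women on hormonal medication for heavy bleeding. The rule does not reach non-hormonal treatment, and inclusion criterion 8a lets hormonal contraception in use for at least 3 months continue.
- *Tests:* women without an in-window result. On the least demanding reading of footnote 8 the diagnostic test may be a transvaginal ultrasound, which leaves the biopsy (reusable if within 12 months) as the main invasive test.

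**4. How long is the uncovered period for a washout patient?**

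Inputs: washout of at least 90 days (13.11.2); one diary cycle of approximately one month (Section 10), taken as 30 days, as 12.1 counts a month.

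Last dose to Day 0 ≥ washout + diary = 90 + 30 = about 120 days.

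This assumes a washout of exactly 90 days (no maximum is set), a last dose taken after consent, and treatment straight after the diary. Further screening or scheduling lengthens it.

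**The case against.** The strongest reply is that this is a coherent device-safety design. The start date agrees in 13.7, footnote 18, Table 23-1 and 18.2. It matches a primary safety endpoint of device- or procedure-related serious events and a causality scale built for the device and procedure. Exposure is also narrow: results can be reused, the one mandatory diagnostic test may be non-invasive, and washout applies to one group of unknown size. The coherence and the narrowness both stand. They explain the rule, but they do not give a serious washout or biopsy event anywhere to be recorded.

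A second reply points to other safeguards. Section 21.7.2 lists unacceptable risk to potential subjects as grounds for stopping, 12.11 asks for source documents from unscheduled visits, and Table 23-1 records concomitant medications and treatments from screening. The CEC charter, the monitoring plan and local IRB rules are separate documents. So a reader should not infer that such an event would reach nobody. The routes that can be seen, however, create no serious adverse event record or reporting duty before Day 0.

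A third reply concerns breadth, and it is right. A reader might infer that all adverse events related to stopping medication should be collected from consent. The documents do not support that. Heavy bleeding with a PBLAC score of at least 150 is needed to qualify, and 14.1.5 treats continuing heavy bleeding as pre-existing. A rule covering all events could turn the qualifying bleed into a reportable event, so the remedy has to stop at serious events.

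**Conclusion.** The gap is real and follows from an explicit rule, not from missing detail. A serious event caused by a study-required step between consent and Day 0 is outside structured safety collection, and the gap is clearest in screen failures. For a woman whose last dose follows consent it lasts at least about 120 days, on the assumptions above. The number of women affected and the event rate are not in the documents, and no estimate is offered. Closing the gap is a cheap improvement that should be made.

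Two stronger readings should be avoided:

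- *Bias in the trial's results.* The primary safety rate counts device- or procedure-related serious events in treated women. Events before the procedure do not belong in it, and efficacy and power do not depend on the collection start.
- *A gap of 210 or 300 days caused by washout.* Table 12-1 keeps a diary valid for 180 days and adds a check after 3 months: "If the qualifying PBLAC diary was completed more than 3 months prior to the date of planned treatment, the investigator must verbally confirm" that heavy bleeding continues. Adding a diary 90 days old at treatment gives 90 + 30 + 90 = 210 days; using the full window gives 90 + 30 + 180 = 300. The time after the diary is scheduling, not a wait required by washout, so neither figure measures what the washout rule imposes.

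**What to change.** Amend five places:

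- **13.7, footnote 18, the screening cell of the adverse event row in Table 23-1, and 18.2:** from the signed consent form, and including screen failures, collect serious adverse events only (criteria of 14.1.2) that are related to a study-required screening test or study-required medication discontinuation.
- **14.3:** apply the 24-hour reporting rule to these events.
- **14.2.4:** add a causality option for events related to a study-required screening test or medication discontinuation.
- **14.1.5:** state that such serious events are not dismissed as pre-existing. Return or continuation of heavy bleeding that does not meet the seriousness criteria stays a pre-existing condition and is not reported.
- **17.5:** list these events separately as pre-procedure events, outside the primary safety endpoint.

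The cost is a little more data entry for screened women, one added causality field and one extra listing. Every consented woman already has an EDC registration and subject number (11.9), so no new system is needed.

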13.8 Complete Blood Count (CBC) and Serum FSH

Complete Blood Count (CBC) and Serum Follicle Stimulating Hormone (FSH) test results may be obtained from the patient medical records if the test was performed 6 months or fewer from the procedure date.

Conduct additional testing as needed to confirm eligibility criteria.

Premenopausal status is to be confirmed by FSH measurement \leq 40 IU/L when the patient is \geq 40 years old.

13.9 Urine Pregnancy Test

Patients will have urine pregnancy test at screening and urine dipstick pregnancy test at the Procedure Visit prior to treatment. Patients with a positive urine pregnancy test result must not be provided investigational treatment. If a patient becomes amenorrheic after the procedure, it will be left to the investigator's judgment whether to consider a pregnancy test to rule out a possible pregnancy for the cause of amenorrhea.

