11.8 Patient Discontinuation and Replacement

Patients are free to terminate their participation (with or without reason) in the study at any time. Likewise, a patient may be terminated from the study by the investigator or the Sponsor, MicroCube, at any time if either investigator or Sponsor determines that it is not in the patient's best interest to continue participation. Enrolled patients that are terminated because of lack of compliance to protocol will not be replaced and will be considered lost to follow-up. If a patient is terminated prior to the 12-month follow up visit, this patient will be considered a treatment failure.

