11.8.1 Reasons for Termination

Every patient should remain in the study until completion of the 36-month follow-up period. Whenever possible, an exit visit should be conducted to record reason(s) for withdrawal, retrieve study materials (PBLAC diaries) and complete relevant visit assessments such: AEs, concomitant medications, patient's menstrual status, NRS for dysmenorrhea-related pain and MIQ. Conceivable reasons for early patient discontinuation may include, but are not limited to, the following:

• Patient Withdrawal (voluntarily terminates consent): Patient participation in this clinical study is voluntary. The patient may choose to discontinue participation (refuse all subsequent testing) at any time without loss of benefits or penalty.

- **Discontinuation:** Patient participation may be discontinued by the patient or investigator because of a treatment modality change, organ transplant, transfer, death or prolonged hospitalization. The Sponsor may also decide to discontinue the testing of the study device.
- **Investigator-initiated Termination:** The Investigator may terminate the patient's participation without regard to the patient's consent if the Investigator believes it is medically necessary. In addition, the following circumstances may require early termination:
 - Patient is unable or unwilling to cooperate with study staff;
 - Emergence of clinically relevant serious adverse events, laboratory abnormalities or other medical condition or situation occurs such that continued participation would not be in the best interest of the patient;
 - Pregnancy
 - o Death
- Exclusion Criterion Discovered After Enrollment: A small number of patients may be enrolled despite meeting an exclusion criterion. This will be documented by the study personnel on the eCRF and will be considered a protocol deviation (PD), not termination.
- Lost-to-Follow-up: This category accounts for patients whose status is unclear because they fail to appear for study assessments/visits without stating intention to terminate consent. The data from this patient is still eligible for the intent-to-treat dataset. Site personnel should make all reasonable efforts to locate and communicate with the patient, at each contact time point, including:

A minimum of three (3) telephone calls to contact the patient should be attempted. Each attempt should be recorded in the patient's medical record, including date, time, and initials of site personnel attempting the contact.

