17.2 Analysis of Primary Efficacy Endpoint at 12-month

The primary efficacy endpoint is binary (success/failure). Success is defined as PBLAC score of \leq 75 at the 12-month follow-up assessment without incidence of additional interventions or treatments for bleeding prior to the 12-month follow-up visit. The proposed study's primary hypothesis is:

Null Hypothesis (H₀) = $p_{minitouch} \le OPC$

Alternate Hypothesis (H₁) = p_{minitouch} > OPC

where p_{minitouch} is the Minitouch Endometrial Ablation System success rate and OPC is 66% which is the FDA identified objective performance criterion (OPC) for global endometrial ablation (GEA) devices.

The exact binomial test will be conducted to compare the investigational device success rate to OPC minimum success rate for effectiveness. To achieve study success the measured success rate should exceed the 66% OPC.

ITT with imputation will be utilized to test the primary hypothesis, such that all missing data are failures for the primary endpoint. The following imputation techniques will be conducted for sensitivity analysis:

- Multiple Imputation (MI) using fully conditional specification (FCS) method, in which logistic regression is used to predict whether the missing value is likely to be a success or failure. The number of imputations will depend on the fraction of missing information.
- Tipping point, in which the numbers of successes or failures amongst missing data necessary to meet the primary endpoint hypothesis are determined.

Fisher-Freeman-Halton test will be conducted to compare the success rates between investigational sites. Results will also be stratified and compared across relevant baseline characteristics including demographics.

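### Section 13.9 and Table 23-1 footnote 10 give different rules for pregnancy testing when a patient becomes amenorrheic after ablation, and the primary endpoint does not say how a pregnancy is classified

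*Combined protocol and SAP*

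**What the plan says.** **Testing rule.** Section 13.9 (Urine Pregnancy Test) leaves the decision in a patient who becomes amenorrheic after the procedure to the investigator's "judgment whether to consider a pregnancy test to rule out a possible pregnancy for the cause of amenorrhea". In Section 23, Table 23-1, footnote 10 to the urine pregnancy row reads: "if study patient becomes amenorrheic at any time post-procedure, a urine pregnancy test should be administered". Footnote 11, on the same row, says "Conduct urine pregnancy tests as needed during follow-up" and does not mention amenorrhea. The row itself is marked only at screening and at the procedure visit.

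**Endpoint rule.** Under Section 17.2 a patient is a success if the 12-month PBLAC score is 75 or lower "without incidence of additional interventions or treatments for bleeding prior to the 12-month follow-up visit". Pregnancy is not mentioned there. Section 11.8.1 lists pregnancy under the statement that "the following circumstances may require early termination". Section 11.8 adds: "If a patient is terminated prior to the 12-month follow up visit, this patient will be considered a treatment failure". Missing 12-month data are failures in the primary test (Section 17.2).

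**Safety context.** Table 14-1 lists pregnancy-related complications among the rare anticipated adverse device effects. Section 14.1.2 counts fetal distress, fetal death and congenital abnormality as serious.

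**The concern.** Section 13.9 leaves a decision open and footnote 10 directs a test, both on the same trigger. That trigger is not unusual in this trial. Amenorrhea, a PBLAC score of 0, is one of the named outcome categories in the synopsis, and amenorrhea rates are analysed in Sections 17.1.2 and 17.7. Sites will therefore meet the question whenever the device works as well as it can, and a site that follows Section 13.9 and does not test departs from footnote 10. Section 20.2.2 defines a deviation as any departure from study requirements, so monitors have no consistent basis for classifying that case across about 10 sites.

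Two things are at stake. The main one is safety: whether and when a pregnancy is found would differ by site, and serious events related to the device or procedure are the primary safety endpoint. The lesser one is the primary effectiveness endpoint. Section 13.9 itself recognises pregnancy as a possible cause of amenorrhea, yet the success definition does not separate that cause from a treatment effect.

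**Working it through.** **1. The passages side by side**

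| Place | Trigger | Instruction |
|---|---|---|
| Section 13.9 | Amenorrhea after the procedure | Investigator decides whether to consider a test |
| Table 23-1, footnote 10 | Amenorrhea at any time after the procedure | A test should be given |
| Table 23-1, footnote 11 | None named; follow-up in general | As needed |

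The first two rows share a trigger and differ in instruction, so they conflict. The third names no trigger and is compatible with Section 13.9. It does not resolve the conflict.

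**2. How a pregnancy maps to the endpoint as written**

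- Terminated before month 12 because of the pregnancy: failure (Section 11.8).
- Still in the study, 12-month diary at or below 75, no added bleeding treatment: success (Section 17.2), whether or not the pregnancy is known.
- Still in the study, 12-month diary missing: failure (Section 17.2).

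The second case is a misclassification only if the woman would have scored above 75 without the pregnancy. On the plan's expected success rate of 78%, that is about 1 − 0.78 = 22% of such women, if pregnancy is unrelated to how well the ablation worked. That independence is an assumption; without it the share could be anything up to all of them.

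**3. The plan's own figures**

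Inputs from Section 17.2.1: null 0.66, expected 0.78, one-sided alpha 0.025, power 80%, 10% dropout.

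n = [(1.960 × √(0.66 × 0.34) + 0.842 × √(0.78 × 0.22)) / 0.12]² = 113.26, rounded up to 114.

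113.26 / 0.9 = 125.8, rounded up to 126. (Rounding to 114 before dividing gives 127; the difference does not matter here.)

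The plan's 114 and 126 are reproduced, and nothing in this point changes them.

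**4. What one patient is worth**

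Assume that all 126 patients are in the ITT cohort. Each patient moves the observed rate by 1/126 = 0.79 percentage points. The exact binomial test against 0.66 gives:

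| Successes of 126 | Rate | One-sided p |
|---|---|---|
| 94 | 74.6% | 0.0239 |
| 93 | 73.8% | 0.0374 |
| 92 | 73.0% | 0.056 |
| 91 | 72.2% | 0.082 |

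The test is met at 94 and not at 93. One misclassified woman therefore changes the conclusion only if the count with her included is exactly 94. Two matter only at 94 or 95, and three only at 94 to 96. The number of such women is an assumption, because the documents give no pregnancy rate.

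**The case against.** The strongest reply is that this is a minor wording conflict with almost no bearing on the result. Much of that stands. A patient who wishes to retain fertility is excluded, reliable contraception is required throughout, and a negative test is needed at screening and again on the day of the procedure. For the endpoint to be affected, a pregnancy must also lower the particular diary that counts, in a woman who would otherwise have failed. The conflict is also softer than it might be: footnote 10 makes the two pre-treatment tests mandatory but uses a weaker verb for amenorrhea.

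Three stronger readings are tempting, and the documents do not support them.

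- A reader might infer three competing rules. Footnote 11 names no trigger and fits Section 13.9, so the direct conflict is between Section 13.9 and footnote 10.
- A reader might infer that a woman who tests positive is automatically a failure. Section 11.8.1 says only that pregnancy may require termination, and no passage gives the endpoint status of a pregnant woman who stays in the study.
- A reader might infer that every undetected pregnancy creates a false success. A woman already at or below 75 because of the ablation is a success either way.

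What the reply does not remove is the conflict itself. It is in current text, it concerns a safety check, and its trigger is an outcome that the treatment aims for.

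**Conclusion.** The conflict between Section 13.9 and footnote 10 is certain on the text and should be reconciled, chiefly because sites that follow different passages will act differently on a safety check.

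The endpoint consequence is real but secondary. Success has no pregnancy exception, so a pregnant woman may count as a success or as a failure depending on whether she was terminated before month 12. Its size is 0.8 points per misclassified patient, and it decides the trial only at the 94/126 boundary. That rests on three assumptions: all 126 patients are in the ITT cohort, the pregnancy lowers the 12-month diary to 75 or below, and the woman would otherwise have scored above 75. With no pregnancy rate in the documents, the expected number cannot be computed; the eligibility and contraception rules point to few. A change in the trial's conclusion from this cause is possible but unlikely, and no design figure is affected.

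**What to change.** 1. Reconcile Section 13.9 with footnotes 10 and 11 of Table 23-1 so that one rule for post-procedure amenorrhea applies at all sites. Which testing rule that should be is a clinical decision for the sponsor and investigators, and this review takes no view on it.

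2. Separately, add to Section 17.2 that a 12-month PBLAC score recorded during a known pregnancy is not counted as a success. This is an analysis rule in line with the plan's treatment of missing data as failures. It also settles the status of a pregnant woman who remains in the study.

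The cost is wording in Section 13.9, the two footnotes and Section 17.2. Urine pregnancy tests are already part of the study, and the sample size does not change. The downside of the second change is a possibly slightly lower success rate. It also does not reach undetected pregnancies, and the first change reaches them only so far as the chosen rule leads to testing.
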